8.2 Premature discontinuation of trial product

If a Subject is prematurely discontinued from trial product after randomisation (Visit 14), the Investigator must ensure every possible effort is made to undertake procedures for Visit 40A, as soon as possible.

A "treatment discontinuation" session must be made in the IV/WRS and reason for discontinuation of trial product must be specified in the first part of the End-of-Treatment/Trial form in the eCRF. For CGM and Meal test subgroup the "treatment discontinuation" session must be performed after the meal test has been finalised.

Final drug accountability must be performed. The Subject should be switched to a suitable marketed product at the discretion of the Investigator. The medication should be recorded on the concomitant diabetes medication form in the eCRF, as described in [5.4](#) and [8.4.4](#) at each contact after discontinuation.

The Subject should also complete the follow-up visits (Visit 41 and Phone Contact 42).

In addition, Subjects prematurely discontinued from trial product should continue with the per protocol planned visits after 12 weeks (Visit 26) and 26 weeks (Visit 40) from randomisation depending on when the Subject discontinues trial product. The following assessments are not applicable for prematurely discontinued Subjects at V40: 4-point profile, technical complaints, CGM and meal test, IV/WRS call.

Phone contact after premature discontinuation of trial product:

The Investigator must establish telephone contact with the Subject at least once halfway through the premature discontinuation visit period, if the Subjects discontinue the trial treatment prior to Visit 30. Phone contact will only be recorded in source data and will not be captured in eCRF.

The Subject should be notified that they will be contacted according to the protocol.

All attempts to contact the Subject must be documented in the source document.

At each contact the Investigator should as a minimum capture/evaluate:

- Any assessment of hypo/hyperglycaemic episodes
- Adverse events
- Change in diabetes medication

In case of any findings, these must be captured in the eCRF.

Follow-up contact after premature discontinuation of trial product:

Subjects that prematurely discontinue trial product will be asked to attend an End of Treatment visit (Visit 40A) and follow-up visit 1 (FU1) 7-12 days after visit 40A and follow-up visit 2 (FU2) 30-35 days after V40A.

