6.2 Data collection and data management

The following must be recorded in relation to the meal test:

- Fasting status
- Body weight
- Time and value of SMPG measurement prior to the meal test confirming that the Subject is within the target of 4.0-8.8 mmol/L (71-160 mg/dL)
- Time of blood samples
- Time and dose of insulin injection
- I:carb ratio used for bolus dose calculation (to be recorded at Visit 14 only)
- Start and end-time of standardised liquid meal
- Volume and carb content of standardised liquid meal calculated for consumption (calculated amounts for Visit 14 must also be used at Visit 40)
- Confirmation that the Subject consumed the required volume of the standardised liquid meal
- Volume of standardised liquid meal consumed
- Batch no. of standardised liquid meal consumed
- Hypoglycaemic episode number, time of intervention and amount of glucose rescue treatment if relevant

Laboratory results from meal test data will be loaded directly into the trial database by the central laboratory. The meal test results will not be provided to the Investigator until after end of trial.

7 Premature discontinuation of trial product

If a Subject is prematurely discontinued from trial product after randomisation (Visit 14), the Investigator must ensure every possible effort is made to undertake the CGM and meal test procedures at Visit 40A, similar to the CGM and meal test procedures for Visit 38, Phone contact 39 and Visit 40, as soon as possible after decision of ending treatment.

The CGM and meal test procedure at the premature discontinuation Visit 40A must be performed with the exception that the CGM period can be less than 11 days. The meal test must not be scheduled on the 1st or 7th day after having fitted the sensor. The meal test at Visit 40A should be performed with trial product according to randomisation unless this is not feasible for safety reasons as judged by the Investigator. Confirmation that the meal test was taken with trial product will be recorded in the eCRF.

The CGM and meal test procedure should not be repeated at Visit 40.

Please refer to protocol section [8.2](#) for further procedures related to premature discontinuation of trial product.

8 Withdrawal from trial

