1.2 Scope of the statistical analysis plan

This statistical analysis plan (SAP) is based on the protocol *Efficacy and Safety of Faster-acting insulin aspart compared to NovoRapid® both in Combination with Insulin Degludec in Children and Adolescents with Type 1 Diabetes*, version 5.0 (dated 16 January 2017). The statistical analyses and derivations of endpoints presented in this SAP are almost identical to those described in the protocol. It contains minor clarifications for derivations, calculation of endpoints and analyses as well as a few additions.

The changes to the statistical considerations proposed in this SAP and the reasons for the changes are described in section [3](#) and will be reported in the clinical trial report (CTR).

2 Statistical considerations

General considerations

In general, for endpoints evaluated as a change from baseline and/or where a baseline adjustment is made, baseline is defined as information collected at the randomisation visit (Visit 14). In case a measurement is not available at the randomisation visit, the most recent measurement prior to the randomisation visit will be used as baseline.

Two observation periods are defined, “in trial” and “on treatment”, and it will be specified which period each analysis will use.

- In trial: the observation period from date of randomisation and until last trial -related Subject-site contact. The in trial observation period includes data collected after treatment discontinuation.
- On treatment: the observation period from date of first dose of randomised NovoRapid®/fast-acting insulin aspart and no later than 7 days after the day of last dose of NovoRapid®/fast-acting insulin aspart. The on treatment observation period includes data collected up to and including 7 days after treatment discontinuation.

All primary and secondary efficacy endpoints will be summarised and analysed using the full analysis set (FAS), unless otherwise stated. Safety endpoints will be summarised using the safety analysis set (SAS) and analysed using the FAS, unless otherwise stated.

Presentation of results from a statistical analysis will include the estimated mean treatment effects (LSMeans) for change from baseline, if applicable. Estimated mean treatment differences (or ratios) will be presented together with two-sided 95% confidence intervals for all endpoints analysed statistically.

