2.4.1.1 Efficacy endpoints

All endpoints except insulin dose in this section will be assessed using the FAS and the in trial observation period and repeated using the on treatment observation period. Insulin dose will only be presented using the on treatment observation period.

The following endpoints will be assessed 26 weeks after randomisation:

Change from baseline in 8-point profiles.

PPG increments based on the 8-point profiles will be derived separately for plasma glucose (PG) measurements made 1 hour after the meal. In the following section this distinction will be considered implicit and without further explanation. PPG will be recorded by the Subject as part of two 8-point profiles prior to the visits. PPG increment for each meal (breakfast, lunch, main evening meal) will be derived from the 8-point profile as the difference between PPG values and the PG value before meal in each separate profile. The mean of the derived increments will then be calculated separately for each meal. Mean PPG increment over all meals will be derived as the mean of all corresponding mean meal increments.

- Change from baseline in mean PPG and PPG increment over all three meals

Mean PPG and PPG increment will be analysed separately using a model similar to 1), except with the corresponding baseline value as covariate.

- Change from baseline in individual meal (breakfast, lunch and main evening meal)
PPG and PPG increment from 8-point profile

PPG and PPG increment endpoints for the individual meals (breakfast, lunch, main evening meal) will be analysed separately using a model similar to 1) except with the corresponding baseline value as covariate.

- Change from baseline in mean of the 8-point profile

The mean of the 8-point profile is defined as the area under the profile divided by the measurement time, and is calculated using the trapezoidal method. Mean of the 8-point profile will be analysed using a model similar to 1) except with the corresponding baseline value as covariate.

- Fluctuation in 8-point profile

The fluctuation in the 8-point profile is defined as

$$\frac{1}{T} \int_0^T |PG(t) - \bar{PG}| dt,$$

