2.4.1.2 Safety endpoints

All safety endpoints will be compared using the on treatment observation period. In terms of adverse events, as a minimum, serious adverse events will be tabulated separately also using the in trial observation period.

All events in the in trial observation period will be listed with information about whether it appeared in the on treatment observation period or not.

Classification of Hypoglycaemia:

Treatment emergent: hypoglycaemic episodes will be defined as treatment emergent if the onset of the episode occurs on or after the first day of treatment with investigational medicinal product (IMP) after randomisation, and no later than 1 day after the last day on IMP.

Nocturnal hypoglycaemic episodes: are episodes occurring between 23:00 and 07.00 both inclusive.

[figure not shown]
Hypoglycaemic episodes are classified according to ISPAD's definition of severe hypoglycaemia⁴, as well as Novo Nordisk classification of hypoglycaemia (see [Figure 2-1](#)) and the ADA classification of hypoglycaemia⁵ (see [Figure 2-2](#)).

Novo Nordisk classification of hypoglycaemia in paediatrics

In normal physiology, symptoms of hypoglycaemia occur below a PG level of 3.1 mmol/L (56 mg/dL)⁶. Therefore, Novo Nordisk has included hypoglycaemia with PG levels below this cut-off point in the definition of blood glucose (BG) confirmed hypoglycaemia.

Novo Nordisk uses the following classification (see [Figure 2–1](#)) in addition to the ADA classification:

- Severe hypoglycaemia according to the ISPAD classification⁴: Was the hypoglycaemic episode associated with severe neuroglycopenia, usually resulting in coma or seizure and requiring parenteral therapy (glucagon or intravenous glucose)?
- Symptomatic BG confirmed hypoglycaemia: An episode that is BG confirmed by PG value $< 3.1 \text{ mmol/L (56 mg/dL)}$ **with** symptoms consistent with hypoglycaemia.
- Asymptomatic BG confirmed hypoglycaemia: An episode that is BG confirmed by PG value $< 3.1 \text{ mmol/L (56 mg/dL)}$ **without** symptoms consistent with hypoglycaemia.
- Severe or BG confirmed symptomatic hypoglycaemia: An episode that is severe according to the ISPAD classification⁴ or BG confirmed by a PG value $< 3.1 \text{ mmol/L (56 mg/dL)}$ **with** symptoms consistent with hypoglycaemia.
- BG confirmed hypoglycaemia: An episode that is BG confirmed by a PG value $< 3.1 \text{ mmol/L (56 mg/dL)}$ **with or without** symptoms consistent with hypoglycaemia.

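### In subjects who stop trial product early, the 7-day on-treatment tail lets post-switch meal-test, CGM and 8-point SMPG values count as on randomised insulin

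*SAP*

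**What the plan says.** SAP section 2 (General considerations) defines two observation periods. The on-treatment period starts at the first randomised bolus dose and ends "no later than 7 days after the day of last dose of NovoRapid®/fast-acting insulin aspart". The next sentence spells this out: "The on treatment observation period includes data collected up to and including 7 days after treatment discontinuation". Protocol section 17 has the same definition. SAP 2.4.1.1 then states that all efficacy endpoints except insulin dose "will be assessed using the FAS and the in trial observation period and repeated using the on treatment observation period". It gives no shorter limit for any glucose endpoint.

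Three other provisions bear on this:

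- **Switch of insulin.** Protocol 8.2 says of a subject who stops trial product: "The Subject should be switched to a suitable marketed product at the discretion of the Investigator". Visit 40A follows as soon as possible, with no fixed day relative to the last dose.
- **Use of Visit 40A data.** SAP section 2 (Visit reallocation) moves these values to the next scheduled visit at which the assessment is planned. Its general rule is that every observed value from a randomised subject enters every analysis.
- **Meal test at Visit 40A.** Appendix B section 7 says: "The meal test at Visit 40A should be performed with trial product according to randomisation unless this is not feasible for safety reasons". It adds: "Confirmation that the meal test was taken with trial product will be recorded in the eCRF". The CGM and meal test are not repeated at Visit 40. No rule in the SAP uses the eCRF confirmation.

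For hypoglycaemia, SAP 2.4.1.2 uses a different limit: an episode is treatment emergent if its onset is "no later than 1 day after the last day on IMP".

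**The concern.** A meal-test PPG, a CGM trace and a post-meal SMPG value depend on the bolus injected for that meal. Once the subject takes a marketed bolus, these values say little about the randomised one. The 7-day tail nevertheless classes them as on treatment, and the reallocation rule can carry them to week 26.

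The plan recognises the mechanism. Under the secondary estimand, SAP section 2 explains that the marketed product given after discontinuation may equalise the treatment effect. Post-switch values in the on-treatment repeats would do just that, pulling the arms together in the analyses meant to show the randomised insulins in use. At stake are the on-treatment repeats of the PPG and PPG-increment endpoints from the 8-point profile, and of the meal-test and CGM endpoints.

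**Working it through.** **1. The plan's own figures.** No stated figure depends on this window. The HbA1c power figures reproduce: the standard error is 1.3 × √(2/250) = 0.1163. Step 1 gives 0.40/0.1163 − 1.96 = 1.48, a power of 93.06% (stated: more than 93%). Step 2 gives 0.35/0.1163 − 1.96 = 1.05, a power of 85.32% (stated: 85%). Both concern the in-trial analysis, so this point leaves them alone.

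**2. Which values can fall after the switch but inside 7 days.**

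- *Completers: none.* Week-26 assessments are made at End of Treatment, and the meal test precedes the stop of trial product (Protocol 8.1.9). The first follow-up visit collects no FPG, SMPG profile, CGM or meal test (Protocol 8.1.10.1).
- *Meal test: by exception.* In the subgroup, the IV/WRS discontinuation session comes after the meal test (Protocol 8.2), and the test uses the randomised product unless that is unsafe (Appendix B section 7). A test done off product within 7 days of the last dose is on treatment under the SAP. It is also that subject's only post-baseline meal test.
- *CGM: by exception.* The Visit 40A CGM period leads up to the meal test and may be shorter than 11 days. SAP 2.4.1.1 computes the CGM measures over the whole profile apart from the meal test, and no rule removes time after the last randomised bolus.
- *8-point SMPG: a narrow interval.* Discontinued subjects record profiles on the two days before Visits 26 and 40 (Protocol 8.2). Let L be the day of the last randomised bolus and V the visit day, so the profile days are V−2 and V−1. A profile day is inside the 7-day tail but beyond a 1-day limit when it falls on L+2 to L+7. At least one does so when V lies between L+3 and L+9. The Visit 26 route is narrower still: Protocol 8.2 drops Visit 26 if Visit 40A falls after week 10 and before it, and a week-12 value affects the week-26 result only through imputation.
- *Responder endpoints: none.* Discontinued subjects are non-responders in the on-treatment analysis whatever the window (SAP 2.4.1.1).
- *Confirmatory HbA1c: none.* It uses the in-trial period (SAP 2.3).

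**3. Ceiling on the size.** SAP 2.1 expects fewer than 10% of subjects to discontinue product. That is fewer than 0.10 × 250 = 25 per arm overall, and fewer than 0.10 × 50 = 5 per arm if the same rate holds in the subgroup. Assume that k of n week-26 on-treatment values in a fast-acting aspart arm are post-switch and have the comparator arm's mean. The estimated difference then keeps 1 − k/n of its size:

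| k of 50 | share kept | dilution |
|---|---|---|
| 0 | 100% | 0% |
| 1 | 98% | 2% |
| 2 | 96% | 4% |
| 5 (limit, not reached) | 90% | 10% |

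The documents do not give k. Reaching the limit would need every expected discontinuer to be measured after the switch, within 7 days, with no remaining contrast. A CGM profile only partly after the switch counts as less than one.

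**The case against.** The strongest reply is that the plan already orders these events well. Meal test and CGM are scheduled on randomised product before discontinuation, so off-product values need the safety exception or a deviation. Profiles are listed only around Visits 14, 26 and 40. The 7-day definition is the same in both documents, and the same SAP section uses 7 days for adverse events, so the 1-day hypoglycaemia limit is one precedent among two. The if-adherent estimand is defined only for HbA1c, which leaves the purpose of the other on-treatment repeats to be inferred. The CGM and meal-test subgroup is exploratory and not strictly powered, and every endpoint concerned also has an in-trial analysis.

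Most of this stands, and it keeps the point small. It does not remove it. Protocol 8.2 orders the meal test relative to an IV/WRS session, whereas the window counts from the last dose. Appendix B foresees an off-product test and has it recorded, yet the SAP's general rule still uses the value as on treatment.

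A reader might also infer that FPG is misclassified in the same way. The documents do not support that: basal degludec is titrated to pre-breakfast glucose (Protocol 5.3.1), acts beyond 42 hours (Protocol 3.5) and is common to all arms, while the window is tied to the bolus.

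**Conclusion.** The point holds as a minor one, confined to prematurely discontinued subjects and to the supportive on-treatment repeats for meal-test, CGM and 8-point SMPG endpoints. The ceiling is below 10% of an arm and the likely number is far smaller. The dilution figures assume that post-switch values carry no treatment contrast. The flow-chart rows for FPG and SMPG at Visit 40A cannot be read in the available text, so the frequency of such values there cannot be checked.

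Three wider readings are tempting and not supported:

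- *That every efficacy endpoint is affected.* HbA1c moves slowly, and the responder rules are immune to the window.
- *That the post-meal arm routinely loses its 20-minute dosing at Visit 40A.* Appendix B ties that test to the randomised regimen by default.
- *That 5 of 50, or 25 of 250, estimates the contamination.* These figures bound all discontinuers, not those with a post-switch value in the window.

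No confirmatory conclusion can change.

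**What to change.** Amend the on-treatment definition in SAP section 2:

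1. Keep the 7-day tail for HbA1c and other slow markers.
2. For meal-test, CGM and 8-point SMPG endpoints, count as on treatment only values taken no later than 1 day after the last randomised bolus dose, the limit the SAP already applies to hypoglycaemia.
3. Exclude from the on-treatment analysis any Visit 40A meal test that the eCRF does not confirm as taken with trial product, and any CGM time after the cut-off.
4. Leave the in-trial analyses unchanged. A shorter cut-off for FPG is optional.

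Log the change in SAP section 3, which already records comparable changes of analysis period. Appendix B section 8 gives subjects who withdraw consent the same safety exception without mentioning the confirmation, so check that the field covers them.

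The cost is a few sentences, with no new data collection for discontinued subjects. A few on-treatment values become missing. For the 8-point endpoints the model based on the primary analysis would impute them. The meal-test and CGM endpoints use analysis of variance with no stated imputation, so those values would drop out.

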2.1 Sample size calculation

The primary objective of the trial is to confirm the effect of treatment with meal-time fast-acting insulin aspart in terms of glycaemic control measured by change from baseline in HbA_{1c} 26 weeks after randomisation by comparing it to treatment with meal-time NovoRapid®, both in combination with insulin degludec, using a non-inferiority approach in children and adolescents with type 1 diabetes. The sample size is determined using a non-inferiority limit of 0.4%.

The trial also aims to confirm the effect of treatment with post-meal fast-acting insulin aspart and to confirm superiority of meal-time fast-acting insulin aspart, both in combination with insulin degludec in children and adolescents with type 1 diabetes. This is done using a hierarchical testing procedure with three steps:

Step 1: HbA_{1c} non-inferiority of meal-time fast-acting insulin aspart versus meal-time NovoRapid® both in combination with insulin degludec

Step 2: HbA_{1c} non-inferiority of post-meal fast-acting insulin aspart versus meal-time NovoRapid® both in combination with insulin degludec

Step 3: HbA_{1c} superiority of meal-time fast-acting insulin aspart versus meal-time NovoRapid[®], both in combination with insulin degludec

The sample size is determined to ensure sufficient power for the first step and the second step in the hierarchical testing procedure.

Power for the non-inferiority steps are based on a t-statistic under the assumption of a one-sided test of size 2.5%. A zero mean treatment difference for the comparison between meal-time fast-acting insulin aspart and meal-time NovoRapid[®] is expected, and for the comparison of post-meal fast-acting insulin aspart and meal-time NovoRapid[®] a mean difference of 0.05% in favour of meal-time NovoRapid[®] is expected.

Based on experience from previous trials, and taking into account that the in trial observation period includes data collected after treatment discontinuation, the standard deviation for change in HbA_{1c} is assumed to be 1.3%. With this standard deviation, a sample size of 250 Subjects per group (750 in total) will ensure more than 93% power to show non-inferiority, given that the actual treatment difference is 0%. This sample size will ensure a power of 85% to show non-inferiority of post-meal fast-acting insulin aspart compared to meal-time NovoRapid[®].

The number of Subjects to prematurely discontinue trial product is expected to be less than 10% based on previous trials. The number of Subject to withdraw from trial is expected to be less than 5%.

